### **8.2.3.2 Events of Clinical Interest**

Selected non-serious and serious adverse events are also known as Events of Clinical Interest (ECI) and must be recorded as such on the Adverse Event case report forms/worksheets and reported within 24 hours to the Sponsor either by electronic media or paper. Sponsor Contact information can be found in the Investigator Trial File Binde.

Events of clinical interest for this trial include:

- an overdose of Sponsor's product, as defined in Section 7.2.1 - Definition of an Overdose for This Protocol and Reporting of Overdose to the Sponsor, that is not associated with clinical symptoms or abnormal laboratory results.

- first instance of ALT or AST >500 IU/L
- first instance of ALT or AST >3x baseline AND >100 IU/L
- first instance of alkaline phosphatase >3x ULN

#### **8.2.4 Evaluating Adverse Events**

An investigator who is a qualified physician will evaluate all adverse events with respect to the elements outlined in Table 9. The investigator's assessment of causality is required for each adverse event. Refer to Table 9 for instructions in evaluating adverse events.

**Table 9: Evaluating Adverse Events**

Maximum Intensity	Mild	awareness of sign or symptom, but easily tolerated (for pediatric trials, awareness of symptom, but easily tolerated)
	Moderate	discomfort enough to cause interference with usual activity (for pediatric trials, definitely acting like something is wrong)
	Severe	incapacitating with inability to work or do usual activity (for pediatric trials, extremely distressed or unable to do usual activities)
Seriousness	
A serious adverse event (AE) is any adverse event occurring at any dose or during any use of Sponsor's product that:
 
†Results in death; or
 
†Is life threatening; or places the subject, in the view of the investigator, at immediate risk of death from the event as it occurred [Note: This does not include an adverse event that, had it occurred in a more severe form, might have caused death.]; or
 
†Results in a persistent or significant disability/incapacity (substantial disruption of one's ability to conduct normal life functions); or
 
†Results in or prolongs an existing inpatient hospitalization (hospitalization is defined as an inpatient admission, regardless of length of stay, even if the hospitalization is a precautionary measure for continued observation. (Note: Hospitalization [including hospitalization for an elective procedure] for a preexisting condition which has not worsened does not constitute a serious adverse event.); or
 
†Is a congenital anomaly/birth defect (in offspring of subject taking the product regardless of time to diagnosis); or
 
Is a cancer; or
 
Is associated with an overdose (whether accidental or intentional). Any adverse event associated with an overdose is considered a serious adverse event. An overdose that is not associated with an adverse event is considered a non-serious event of clinical interest and must be reported within 24 hours.
 
Other important medical events that may not result in death, not be life threatening, or not require hospitalization may be considered a serious adverse event when, based upon appropriate medical judgment, the event may jeopardize the subject and may require medical or surgical intervention to prevent one of the outcomes listed previously (designated above by a †).
	
Duration	Record the start and stop dates of the adverse event. If less than 1 day, indicate the appropriate length of time and units	
Action taken	Did the adverse event cause the Sponsor's product to be discontinued?	
Relationship to Sponsor's Product	
Did the Sponsor's product cause the adverse event? The determination of the likelihood that the Sponsor's product caused the adverse event will be provided by an investigator who is a qualified physician. The investigator's signed/dated initials on the source document or worksheet that supports the causality noted on the AE form, ensures that a medically qualified assessment of causality was done. This initialed document must be retained for the required regulatory time frame. The criteria below are intended as reference guidelines to assist the investigator in assessing the likelihood of a relationship between the test drug and the adverse event based upon the available information.
 
The following components are to be used to assess the relationship between the Sponsor's product and the AE; the greater the correlation with the components and their respective elements (in number and/or intensity), the more likely the Sponsor's product caused the adverse event:
	
	Exposure	Is there evidence that the subject was actually exposed to the Sponsor's product such as: reliable history, acceptable compliance assessment (pill count, diary, etc.), expected pharmacologic effect, or measurement of drug/metabolite in bodily specimen?
	Time Course	Did the AE follow in a reasonable temporal sequence from administration of the Sponsor's product? Is the time of onset of the AE compatible with a drug-induced effect (applies to trials with investigational medicinal product)?
	Likely Cause	Is the AE not reasonably explained by another etiology such as underlying disease, other drug(s)/vaccine(s), or other host or environmental factors

Relationship To Sponsor's Product (continued)	The following components are to be used to assess the relationship between the Sponsor's product and the AE: (continued)	
	Dechallenge	
Was the Sponsor's product discontinued or dose/exposure/frequency reduced? If yes, did the AE resolve or improve? If yes, this is a positive dechallenge. If no, this is a negative dechallenge. (Note: This criterion is not applicable if: (1) the AE resulted in death or permanent disability; (2) the AE resolved/improved despite continuation of the Sponsor's product; (3) the trial is a single-dose drug trial); or (4) Sponsor's product(s) is/are only used one time.)

	Rechallenge	
Was the subject re-exposed to the Sponsor's product in this trial? If yes, did the AE recur or worsen? If yes, this is a positive rechallenge. If no, this is a negative rechallenge. (Note: This criterion is not applicable if: (1) the initial AE resulted in death or permanent disability, or (2) the trial is a single-dose drug trial); or (3) Sponsor's product(s) is/are used only one time.) NOTE: IF A RECHALLENGE IS PLANNED FOR AN ADVERSE EVENT WHICH WAS SERIOUS AND WHICH MAY HAVE BEEN CAUSED BY THE SPONSOR'S PRODUCT, OR IF RE-EXPOSURE TO THE SPONSOR'S PRODUCT POSES ADDITIONAL POTENTIAL SIGNIFICANT RISK TO THE SUBJECT THEN THE RECHALLENGE MUST BE APPROVED IN ADVANCE BY THE U.S. CLINICAL MONITOR AND THE INSTITUTIONAL REVIEW BOARD/INDEPENDENT ETHICS COMMITTEE.

	Consistency With Trial Treatment Profile	
Is the clinical/pathological presentation of the AE consistent with previous knowledge regarding the Sponsor's product or drug class pharmacology or toxicology?

The assessment of relationship will be reported on the case report forms /worksheets by an investigator who is a qualified physician according to his/her best clinical judgment, including consideration of the above elements.
		
Record one of the following:		Use the following scale of criteria as guidance (not all criteria must be present to be indicative of a Sponsor's product relationship).
Yes, there is a reasonable possibility of Sponsor's product relationship.		There is evidence of exposure to the Sponsor's product. The temporal sequence of the AE onset relative to the administration of the Sponsor's product is reasonable. The AE is more likely explained by the Sponsor's product than by another cause.
No, there is not a reasonable possibility of Sponsor's product relationship		Subject did not receive the Sponsor's product OR temporal sequence of the AE onset relative to administration of the Sponsor's product is not reasonable OR there is another obvious cause of the AE. (Also entered for a subject with overdose without an associated AE.)

### 8.2.5 Sponsor Responsibility for Reporting Adverse Events

All Adverse Events will be reported to regulatory authorities, CPP/ANSM and investigators in accordance with all applicable global laws and regulations.

## 9. LABELING, PACKAGING, STORAGE AND RETURN OF CLINICAL SUPPLIES

### 9.1 Investigational Product

EBR is an HCV NS5A inhibitor and GZR is an HCV NS3/4A protease inhibitor which is direct-acting antiviral agents against the hepatitis C virus.

The investigator shall take responsibility for and shall take all steps to maintain appropriate records and ensure appropriate supply, storage, handling, distribution and usage of investigational product in accordance with the protocol and any applicable laws and regulations.

Clinical Supplies will be provided by the Sponsor as summarized in Table 10

**Table 10 : Summary product information**

Route of Administration	Dosage Form / Strength	Clinically Relevant Nonmedicinal Ingredients
oral	Tablet 50 mg elbasvir and 100 mg grazoprevir	Lactose monohydrate For a complete listing see Dosage Forms, Composition and Packaging section.

### 9.2 Dosage and Administration

EBR/GZR is a two-drug, fixed-dose combination product containing 50 mg of elbasvir and 100 mg of grazoprevir in a single tablet. The recommended dosage of EBR/GZR is one tablet taken orally once daily with or without food [see Clinical Pharmacology (section 2.2.2)]. EBR/GZR is used in combination with ribavirin in certain patient populations (see Table 1). When administered with EBR/GZR, the recommended dosage of ribavirin in patients without renal impairment is weight-based administered in two divided doses with food. For further information on ribavirin dosing and dosage modifications, refer to the ribavirin prescribing information.

Treatment Regimen and Duration of Therapy Relapse rates are affected by baseline host and viral factors and differ between treatment regimens and durations for certain subgroups [see Clinical Studies (section 2.3)]. Table below provides the recommended EBR/GZR treatment regimen and duration based on the patient population and genotype in HCV mono-infected and HCV/HIV-1 co-infected patients with or without cirrhosis and with or without renal impairment including patients receiving hemodialysis.

**Table 11 : Recommended Dosage Regimens and Durations for EBR/GZR for treatment of HCV genotype 1 or 4 in Patients with or without Cirrhosis**

PATIENT POPULATION	TREATMENT	DURATION
Genotype 1a : treatment-naïve or PegIFN/RBV-experienced without baseline NS5A polymorphisms	EBR/GZR	12 weeks
Genotype 1a : treatment-naïve or PegIFN/RBV-experienced with baseline NS5A polymorphisms	EBR/GZR + RBV	16 weeks
Genotype 1b : treatment-naïve or PegIFN/RBV-experienced	EBR/GZR	12 weeks
Genotype 1a or 1b : PegIFN/RBV/Protease inhibitor experienced	EBR/GZR + RBV	12 weeks
Génotype 4 : Treatment naïve	EBR/GZR	12 weeks
Génotype 4 : PegIFN/RBV-experienced	EBR/GZR + RBV	16 weeks

### 9.3 Packaging and Labeling Information

ZEPATIER® (elbasvir and grazoprevir) is a fixed-dose combination tablet for oral administration containing 50 mg of elbasvir and 100 mg of grazoprevir. The beige and oval shaped film-coated tablets bear the inscription "770" on one side and are smooth on the other. ZEPATIER® is available in two blister packs of 28 tablets.

Clinical supplies will be affixed with a clinical label in accordance with regulatory requirements.

Subjects will receive Open Label EBR(50mg)/GZR(100mg) at the baseline visit.

### 9.4 Clinical Supplies Disclosure

This trial is open-label; therefore, the subject, the trial site personnel, the Sponsor and/or designee are not blinded. Drug (name, strength) is included in the label text; random code/disclosure envelopes or lists are not provided.

## **9.5 Storage and Handling Requirements**

Clinical supplies must be stored in a secure, limited-access location under the storage conditions specified on the label. EBR/GZR bottle should be stored at controlled room temperature until required for administration. Controlled room temperature is defined as 25 °C, excursions are permitted between 15°C and 30°C.

Receipt and dispensing of trial medication must be recorded by an authorized person at the trial site.

Clinical supplies may not be used for any purpose other than that stated in the protocol.

## **9.6 Returns and Reconciliation**

The investigator is responsible for keeping accurate records of the clinical supplies received from the Sponsor or designee, the amount dispensed to and returned by the subjects and the amount remaining at the conclusion of the trial.

For all trial sites, the local country Sponsor personnel or designee will provide appropriate documentation that must be completed for drug accountability and return.

## **9.7 Study drug adherence and drug Accountability**

Subjects must be instructed to bring back all bottles of study medications in the original container at every study visit after Day 1 through the end of treatment.

Study medications will be reconciled using medication pill count at every study visit after Day 1 by the investigator or designee in order to monitor the subject's adherence with the medication regimen.

## **9.8 Drug Interactions**

Co-administration of EBR/GZR and OATP1B inhibitors may significantly increase grazoprevir plasma concentrations and is contraindicated.

The concomitant use of EBR/GZR and strong CYP3A inducers or efavirenz may significantly decrease elbasvir and grazoprevir plasma concentrations and may lead to a reduced

therapeutic effect of study drug. Therefore, the use of EBR/GZR with strong CYP3A inducers or efavirenz is contraindicated.

The concomitant use of EBR/GZR and moderate CYP3A inducers may decrease elbasvir and grazoprevir plasma concentrations and may lead to a reduced therapeutic effect of study drug. Therefore, the use of EBR/GZR with moderate CYP3A inducers is not recommended.

The concomitant use of EBR/GZR and strong CYP3A inhibitors increases elbasvir and grazoprevir concentrations. Co-administration of EBR/GZR with certain strong CYP3A inhibitors is not recommended.

The plasma concentration of grazoprevir is increased if EBR/GZR is co-administered with cyclosporine. Co-administration with cyclosporine is contraindicated.

Co-administration of EBR/GZR with P-gp inhibitors is expected to have a minimal effect on the plasma concentrations of EBR/GZR.

Grazoprevir is a substrate of OATP1B drug transporters. Co-administration of EBR/GZR with drugs that inhibit OATP1B transporters may result in a significant increase in the plasma EBR/GZR concentration of grazoprevir. As such, co-administration of EBR/GZR with OATP1B inhibitors is contraindicated.

Investigational agents are not permitted.

The following medications/therapies are contraindicated in this study

Strong CYP3A/P-gp inhibitors, including but not limited to

- Antibiotics: clarithromycin, erythromycin, telithromycin
- Antifungals: itraconazole, ketoconazole, voriconazole
- Antihypertensives: nifedipine
- nefazodone

Strong and moderate CYP3A/P-gp inducers, including but not limited to

- Anti-infectives: nafcillin, rifampin
- Anticonvulsants: carbamazepine, phenytoin, phenobarbital
- bosentan
- modafinil
- St. John's Wort

OATP inhibitors, including but not limited to

- Immunosuppressants: cyclosporine
- Anti-infectives: rifampin
- Diabetes agents: glibeclamide, glyburide
- Lipid lowering agents: gemfibrozil
- eltrombopag
- lapatinib
- grapefruit/grapefruit juice

All HMG-CoA reductase inhibitors (statins)

In general, CYP3A4 substrates with narrow therapeutic ranges (e.g. warfarin, amiodarone, flecainide, propafenone, quinidine, fentanyl, sildenafil or tadalafil when used for the treatment of pulmonary arterial hypertension) are not prohibited but their levels can potentially be increased by approximately 30% when co-administered with study drugs.

### ***Diet Consideration***

EBV/GZR can be taken without regard to food. Intake of grapefruit or grapefruit juice is contraindicated during the treatment period of the trial.

## **10. STATISTICAL ANALYSIS PLAN**

### **10.1 Sample size estimation**

To evaluate the efficacy of of Elbasvir/Grazoprevir Fixed-Dose Combination for 8 Weeks in Treatment-Naïve for HCV GT1b-Infected Patients, with non-severe fibrosis, the sample size estimation was performed according to the precision of 95% confidence interval of the primary outcome measured by the proportion of subjects with sustained viral response 12 weeks after cessation of treatment. Considering an efficacy at 96%, n=120 patients will be able to obtain an exact 95% confidence interval with a lower bound greater than 91.5%, which could be considered as the minimal efficacy obtained in several works presented recently in literature.

An exploratory interim analysis will be conducted. More precisely, we want to evaluate whether after the inclusion of the first 50 patients, the expected SVR12 rate of 96% always seems a robust and possible assumption. In order to better estimate the rate of responders treated and to ensure that with 120 patients the lower limit of the 95% confidence interval is well above 91.5%, it seems reasonable and relevant to consider early intermediate analysis, without inflation of type I error.

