**Statistical Methods :**

The sample size estimation was performed according to the precision of 95% confidence interval of the primary outcome measured by the proportion of subjects with sustained viral response 12 weeks after cessation of treatment. Considering an efficacy at 96%, **n=120 patients** will be included in this study and will be able to obtain an exact 95% confidence interval with a lower bound greater than 91.5%, which could be considered as the minimal efficacy obtained in several works presented recently in literature.

The primary efficacy endpoint for the study is the proportion of subjects with SVR12 in all enrolled and treated subjects.

Secondary efficacy endpoints include SVR4 and SVR24, and the proportion of subjects with virologic failure.

Safety endpoints will be analyzed by the number and percent of subjects with events or abnormalities for categorical values or 8-number summary (n, mean, standard deviation, median, Q1, Q3, minimum, maximum) for continuous data.

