## 4. STUDY DESIGN

### 4.1 Trial Design

This is a multi-site, open-label evaluating the efficacy of GRAZOPREVIR (100 mg - second-generation protease inhibitor) in combination with ELBASVIR (50 mg - NS54A inhibitor), in treating non-cirrhotic, treatment-naïve (TN) subjects with chronic hepatitis C (CHC) infection with genotypes 1b to be conducted in conformance with Good Clinical Practice.

Approximately 120 subjects will be enrolled in this study.

There will be one treatment group with EBR/GZR (50/100 mg) once daily without regards to food for 8 weeks.

Several measures have been included in order to limit risk to the study subject.

- Subjects will be discontinued from all study therapy (where applicable) if they meet any of the criteria for discontinuation (details in Section 5.4).
- Study therapy will also be discontinued for subjects who meet criteria for virologic failure (defined in section 2.8.4).
- In the event there is an unacceptable rate of virologic failure (details in section 2.8.4) or discontinuation of study medications due to safety concerns, the treatment or the entire study may be terminated.

Specific procedures to be performed during the trial, as well as their prescribed times and associated visit windows, are outlined in the Trial Flow Chart - Table 7 Details of each procedure are provided in Section 8.1 – Trial Procedures.

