### **10.3 Analyses for the primary outcome**

To evaluate the efficacy of Elbasvir/Grazoprevir Fixed-Dose Combination for 8 Weeks in Treatment-Naïve for HCV GT1b-Infected Patients, with non-severe fibrosis as measured by the proportion of subjects with sustained viral response 12 weeks after cessation of treatment (SVR 12), the proportion of patients presenting a sustained viral response 12 weeks after cessation of treatment (HCV RNA < LLOQ 12 weeks after cessation of treatment) will be presented with the associated 95% confidence interval estimated using binomial exact distribution (exact confidence interval). The lower-bound of the confidence intervals will be studied and analyzed regardless assumptions proposed for sample size estimation.

A detailed description of patients not assume SVR12 will be proposed according to clinical relevance using age, gender, BMI, fibrosis score, viral charge and additional endpoints as necessary

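### At 96% efficacy, 120 patients give an exact 95% lower bound of about 90.5% to 90.8%, not above 91.5%; the stated precision is reached only from 116/120 (96.7%)

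*Combined protocol and SAP*

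**What the plan says.** The trial has a single arm. Section 4.1 states "There will be one treatment group with EBR/GZR (50/100 mg) once daily" and "Approximately 120 subjects will be enrolled in this study". The sample size rests on the precision of the SVR12 estimate. Section 10.1 reads: "Considering an efficacy at 96%, n=120 patients will be able to obtain an exact 95% confidence interval with a lower bound greater than 91.5"%. It describes the 91.5% as the minimal efficacy seen in recent literature. The Statistical Methods part of the synopsis makes the same claim: 120 patients "will be able to obtain an exact 95% confidence interval with a lower bound greater than 91.5"%.

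The next paragraph of section 10.1 adds an exploratory interim analysis after the first 50 inclusions. One of its aims is "to ensure that with 120 patients the lower limit of the 95% confidence interval is well above 91.5"%.

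Section 10.3 fixes the method for the primary outcome, a "95% confidence interval estimated using binomial exact distribution (exact confidence interval"), and adds: "The lower-bound of the confidence intervals will be studied and analyzed regardless assumptions proposed for sample size estimation". No section gives a power, a probability of reaching the bound, or a decision attached to 91.5%.

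**The concern.** This sentence is the only quantitative justification for the number of patients. It names an assumed rate, a sample size, an interval method and a result, so it can be checked directly, and the result does not follow from the other three.

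An ethics committee or other reader would take from it that a drug performing as assumed will give an interval clear of 91.5%. In fact the assumed rate puts the design just short of that line. The bound tolerates 4 failures, while 120 × 0.04 = 4.8 are expected. The plan also does not say how a bound below 91.5% would be read.

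**Working it through.** **Inputs.** Assumed SVR12 96% and n = 120 (section 10.1; section 4.1 says approximately 120). Exact binomial 95% interval (section 10.3), taken as two-sided with 2.5% per tail, in line with the two-sided convention of section 10.2. Reference value 91.5% (section 10.1).

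**Formula.** For x responders out of n, the Clopper-Pearson limits are

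- lower = the 0.025 quantile of Beta(x, n − x + 1)
- upper = the 0.975 quantile of Beta(x + 1, n − x)

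**Step 1: try to reproduce the plan's figure.** 0.96 × 120 = 115.2, which is not a whole number, so three readings are possible.

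| Responders | Observed rate | Exact 95% CI | Lower bound above 91.5%? |
|---|---|---|---|
| 115/120 | 95.8% | 90.54% to 98.63% | no |
| 115.2/120 (fractional) | 96.0% | 90.77% to 98.73% | no |
| 116/120 | 96.7% | 91.69% to 99.08% | yes |

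The plan's figure is reproduced only by rounding up to 116, and 116/120 is no longer 96%.

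**Step 2: could another interval explain it?** Lower limits at 115/120: Wilson 90.62%, Jeffreys 91.11%, mid-p 91.01%, Agresti-Coull 90.37%, one-sided 95% exact 91.44%. All fall short. The Wald limit (92.26%) exceeds 91.5% but is not exact. The one-sided exact limit reaches 91.66% only with the fractional count, and it is not the two-sided interval assumed here.

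**Step 3: chance of a lower bound above 91.5% at n = 120.** The bound requires at least 116 responders, that is, at most 4 failures. With F ~ Binomial(120, 1 − p), P(F ≤ 4) at p = 0.96 is

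0.0075 + 0.0373 + 0.0924 + 0.1515 + 0.1846 = 0.473

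| True SVR12 | P(lower bound > 91.5%) |
|---|---|
| 95% | 27.8% |
| 96% | 47.3% |
| 97% | 70.8% |
| 98% | 90.6% |

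The expected lower bound at a true 96% is 90.85%.

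**Step 4: what the interim look can show.** A result exactly on assumption, 48/50, has an exact 95% CI of 86.3% to 99.5%. It leaves 4 − 2 = 2 failures for the remaining 70 patients. P(at most 2 failures in 70) at a true 96% is 46.6%, about the same as at the start.

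**Step 5: dependence on the denominator.** With 121 patients, 116 responders give a lower bound of 90.62% and miss. With 118, 114 responders suffice (91.55%). With 117, four failures (113/117) give 91.48% and miss, so only three are allowed. A count of 116 is therefore valid only if exactly 120 patients are analysed.

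**The case against.** The fair reply is that the gap is one patient. A planner who rounded 115.2 up to 116 would obtain 91.69% and write what section 10.1 says. That probably explains the sentence, but it does not make it true at 96%.

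Two stronger readings are tempting, and neither is supported.

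- A reader might call 47% the power of the trial, or conclude that the trial is more likely than not to fail. Section 10.1 sizes the study on precision, and section 10.3 says the bound will be examined whatever was assumed for sizing. There is no hypothesis or success rule to fail. Nor is a bound below 91.5% the most likely result in the sense of a single count: at a true 96% the most probable count is 116 (18.5%, against 17.8% for 115), and 116 meets the bound. Only the pooled outcomes favour a shortfall, 52.7% to 47.3%.
- A reader might connect the 96% with Table 4, which prints 97% beside 29/31. No section says that Table 4 is the source of the 96%. The entry is a separate clerical slip: section 2.7 correctly gives 29/31 as 94% and 28/29 as 97%, the latter for F0-F2.

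It is also fair to say that the interim analysis is labelled exploratory and carries no decision, and that the final exact interval will be valid whatever section 10.1 says. Both points stand. They limit the consequence to the planning statement but do not correct it.

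**Conclusion.** The precision claim in section 10.1 and the synopsis is wrong as written. At the assumed 96%, the exact two-sided 95% lower bound with 120 patients is 90.5% (115/120) or 90.8% (fractional count), roughly 0.7 to 1 percentage point below the stated 91.5%. The claim becomes true at 116/120, or 96.7%. At a true 96% the chance of a bound above 91.5% is 47%, so the planned precision is close to a coin toss.

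These figures assume exactly 120 patients in the Full Analysis Set, independent outcomes, and a 96% that already counts missing SVR12 values as failures. Section 10.2 treats a missing value as a failure unless successes bracket it, and section 5.4.1 does not replace patients who discontinue. If the 96% describes only patients with data, the chance is lower. As an illustration, and not from the documents, 2% missing and counted as failures gives 0.96 × 0.98 = 94.1% and a chance of about 16%.

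**What to change.** 1. In section 10.1 and the synopsis, replace the precision sentence with: *With 115/120 SVR12 the exact 95% CI is 90.5% to 98.6%. A lower bound above 91.5% needs at least 116/120 (91.7% to 99.1%), which has probability 47% if the true rate is 96%, 71% at 97% and 91% at 98%.*
2. In the interim paragraph of section 10.1, drop the idea of ensuring the bound. Say instead that the exploratory look assesses whether a lower bound above 91.5% is still attainable.
3. If section 10.3 is to refer to the 91.5% minimum, state it as an exact 95% lower bound above 91.5% in the Full Analysis Set, and not as a fixed count of 116, because the number analysed may not be 120.
4. Separately, correct the elbasvir/grazoprevir entry in Table 4 to agree with section 2.7.

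The cost is wording and a less favourable stated precision. No extra patients are needed, and neither the estimator nor the treatment changes.
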